2 OBJECTIVE

To examine the efficacy and safety of posterior wall isolation (PWI) within the region of the PV component in conjunction with pulmonary vein (PV) isolation (PVI) versus PVI alone using cryoballoon ablation for the treatment of patients with symptomatic paroxysmal atrial fibrillation (PAF) during long-term follow-up

3 STUDY ENDPOINTS

3.1 PRIMARY EFFICACY ENDPOINT

To investigate the recurrence of AF following PVI+PWI versus PVI alone using cryoballoon ablation in patients with symptomatic PAF

3.2 SECONDARY EFFICACY ENDPOINT

To investigate the recurrence of all atrial arrhythmias following PVI+PWI versus PVI alone using cryoballoon ablation in patients with symptomatic PAF

3.3 SAFETY ENDPOINTS

[figure not shown]
To examine the acute and long-term adverse event rates associated with PVI+PWI versus PVI alone using cryoballoon ablation in patients with symptomatic PAF, including but not limited to the following:

- Vagal nerve injury resulting in GI or esophageal dysmotility
- Heart failure
- Stroke or transient ischemic attack
- Esophageal injury or atrioesophageal fistula
- Vascular access complications (*e.g.* groin site issues, vascular injury)
- Cardiac perforation, tamponade or pericardial effusion
- Pericarditis
- Phrenic nerve injury (unresolved at discharge)
- Pulmonary vein stenosis
- Major bleeding
- Myocardial infarction
- Death

4 INTRODUCTION AND RATIONALE

Cryoballoon ablation has emerged as a safe and effective strategy for the treatment of atrial fibrillation (AF)^{1,2}, and based on growing evidence,^{2,3,4} it recently received an initial rhythm control strategy ('first-line' therapy) indication by the Food and Drug Administration. Pulmonary vein (PV) isolation (PVI) guided typically by cryoballoon PV occlusion remains the cornerstone of cryoballoon ablation. Although single-procedure freedom from recurrent AF following such an approach has been reported to be as high as 82% at 12 months,^{5,6} the success appears to be markedly diminished in the range of 50–60% during long-term follow-up.⁷ This in part may be related to the inherent limitations of cryoballoon ablation which often yields an ostial (distal) level PVI.⁸ Along these lines, prior investigations have found wide-area antral PVI encompassing the PV component (*i.e.*, the region of the posterior wall lying between the PVs) to be superior to ostial PVI.⁹ Other more recent studies involving the cryoballoon have demonstrated marked improvements in clinical efficacy associated with concomitant PVI and posterior wall isolation (PWI) within the region of the PV component as compared to PVI alone, in patients with persistent AF.^{10,11,12,13} Though widely-practiced, this approach has not been formally investigated in patients with symptomatic paroxysmal AF (PAF). Given the mechanistic similarities between persistent and PAF, we hypothesize that similar benefits may also be observed with PVI+PWI in the patients with PAF. Yet, given the relative infrequency of breakthrough/recurrent arrhythmias in patients with PAF, to detect a significant difference, large sample sizes and extended follow-up (>24 months) are likely needed. Hence, the aim of this retrospective, observational study is to examine the clinical efficacy and safety of PVI alone versus PVI+PWI using cryoballoon ablation (Figure 1), in a large cohort of patients with symptomatic PAF beyond 36 months of follow-up.

FIGURE 1. 3-D electro-anatomic maps created following cryoablation of AF illustrating the two proposed ablation strategies, including PVI (A) versus PVI+PWI to ablate and target the PV component (B). Voltage cutoff set to: 0.1 mV (the maps were created using CARTO; Biosense Webster, Inc, Irvine, CA). Areas shown in red correspond to ablated sites (voltage <0.1 mV) and those in pink correspond to unablated regions with normal voltage. Abbreviations: LIPV, denotes left inferior pulmonary vein; LSPV, left superior pulmonary vein; PVc, pulmonary venous component; RIPV, right inferior pulmonary vein and RSPV, right superior pulmonary vein.

4.1 EMBRYOLOGIC EVIDENCE

The PV component of the posterior left atrial wall shares a common primordial origin with the PVs.¹⁴ The embryologic origin of the four PVs and the PV component can be traced back to the mediastinal myocardium derived from a mid-pharyngeal strand at 6 weeks of gestation.¹⁵ Early on during development, a single primitive vein returns blood from the lungs to the common trabeculated atrium.¹⁶ As the interatrial septum forms, the single vein divides twice to give rise to the four PVs. As the PV ostia migrate away from one another, the smooth tissue of the posterior left atrial wall forms.¹⁶ Although this region is anatomically contiguous with the surrounding trabeculated tissue from the primitive left atrium, its embryologic origin results in electrophysiologic properties that are more similar to the muscular PV sleeves than the immediately adjacent atrial roof or floor ('true' posterior wall).¹⁶

During embryogenesis, the single vein and its surrounding tissue (in addition to the Bachmann's bundle and sinus venosus-derived structures) demonstrate the expression of genes responsible for development of cardiac conduction system.¹⁷ Although expression of these genes decreases during embryogenesis, it is hypothesized that their continued low-level expression may explain why certain regions within the atria are more commonly the site of origin of focal ectopy.¹⁷ These embryologic characteristics would certainly explain the well-accepted clinical observation that AF is frequently initiated by ectopic beats arising from the PVs¹⁸ and the increasingly reported observation that ectopic beats from the left atrial posterior wall can similarly initiate AF.¹⁹

4.2 ANATOMIC EVIDENCE

A visual examination of the PV component and the orientation of its myofibrils suggests direct continuity between this region and the PV antra as does a gross anatomical assessment of certain left atrial morphologies (**Figure 2**). Meanwhile, underneath the smooth endocardial surface of the PV component, numerous subendocardial and subepicardial muscular bundles traverse with varying fiber orientation.¹⁶ Fibers immediately surrounding the PVs typically encircle the veins, whereas those in the subepicardial aspect of the posterior wall are comprised of the septo-pulmonary bundle and display a more vertical or oblique orientation (**Figure 3**).¹⁶ Immediately adjacent to the lateral aspect of the septo-pulmonary bundle are found transversely

oriented fibers which extend to the left PV ostia. It is this change in orientation that is believed to promote anisotropic conduction and therefore reentry.¹⁶

[figure not shown]
[figure not shown]

FIGURE 3. An illustration of the human inter-atrial and intra-atrial muscular bundles of the posterior left atria wall (illustration borrowed from: Clarke, et al. *J Cardiovasc Electrophysiol* 2021 Jul 13. doi: 10.1111/jce.15164. Online ahead of print). Abbreviations: LAA, denotes left atrial appendage; LIPV, denotes left inferior PV; LSPV, left superior PV; RIPV, right inferior PV; RSPV, right superior PV and SVC, superior vena cava.

Markides *et al.*²⁰ found that in patients with PAF, this juxtaposition of fiber orientations was associated with isochronal crowding and functional block depending on the direction of wave front propagation during sinus or paced rhythm. Similarly, mapping of fibrillatory waves during

cardiac surgery in patients with AF has revealed simultaneous propagation of longitudinally dissociated fibrillation waves which are separated by continuously changing lines of block.²¹ These lines of block are once again most densely packed in the PV component, leading to the highest degree of block and dissociation and the lowest incidence of wave front boundaries formed by collision.²²

4.3 ELECTROPHYSIOLOGIC EVIDENCE

As discussed, the PV component is derived from tissues other than the primitive cardiac tube.^{14,23} Hence, the PV component is believed to be related more to PV versus atrial tissue. Some studies have suggested that these tissues share more in common with the sinoatrial nodal myocytes, displaying higher diastolic calcium contents and propensity to spontaneous depolarization.²⁴ Furthermore, the PV component exhibits increased conduction abnormalities,²⁵ a higher incidence of delayed after depolarizations and larger late sodium and intracellular and sarcoplasmic reticulum Ca⁺⁺ contents, but a smaller inward rectifier potassium currents^{20,26} and a reduced resting membrane potential.^{26,27} The posterior wall and the PV myocytes are also characterized by shorter action potential durations and slower phase 0 upstroke velocities.²⁷ As such, the PV component is believed to be the site of collision of activation wave fronts as they sweep across the left atrial dome.¹⁴ Along these lines, Mandapati *et al.*²⁸ found this region of the left atrium to be responsible for 80% of high-frequency rotors in an isolated sheep heart model.²⁹ Similarly, mapping in humans often localizes stable rotors or focal sources²⁹ as well as complex fractionated electrograms³⁰ in the posterior wall and the left atrial roof. The PV component has in fact been shown to be a common source of triggers accounting for up to ~40% of non-PV triggers in patients with AF.³¹

Lastly, the PV component is also the site of the main autonomic ganglionic plexi related to the left atrial dome (*i.e.*, the superior left atrial ganglionated plexus) which is believed to modulate extrinsic cardiac innervation and facilitate the occurrence of AF in a hyperactive autonomic state.^{13,32} As such, it is believed that catheter ablation of the PV component also greatly attenuates the input of these plexi to the PVs, interrupting the vagosympathetic input to the ligament of Marshall and the inferior left ganglionated plexus which have been highly implicated in the pathogenesis of AF.^{13,32}

5 STUDY DESIGN

All consecutive patients with an age >18 years and symptomatic PAF who underwent a first-time cryoballoon ablation using either PVI alone or PVI+PWI with at least 36 months of follow-up by a single operator ([name]) between 1/2014 and 12/2018 at Mercy General Hospital, will be included in this retrospective, non-randomized study. Consistent with the current definitions,³³ all patients with persistent or long-standing persistent/permanent AF will be excluded from this analysis. Baseline patient demographics, procedural and clinical findings and outcomes will be exclusively obtained from retrospective chart reviews within the Cerner electronic medical record by the study investigator or sub-investigators listed on the protocol.

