6 SAMPLE SIZE

The target sample size for this study is approximately 1,000 patients.

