7 STATISTICAL METHODS

Baseline patient demographics, procedural and clinical characteristics will be recorded for the entire cohort. Continuous variables will be analyzed using the two-sample *t* test or Mann-Whitney test for parametric and non-parametric variables, respectively. The χ^2 or Fisher exact test will be used for parametric or non-parametric categorical variables, respectively. For freedom from recurrent atrial arrhythmias, a Kaplan-Meier modeled analysis will be performed. For all analyses, P-values will be two-sided and a $P<0.05$ will be considered statistically significant. The analyses will be conducted with use of SPSS Version 20 (IBM SPSS Statistics, Chicago, IL).

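### Does 'first-time cryoballoon ablation' let patients with an earlier radiofrequency or surgical AF ablation into the comparison?

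*Combined protocol and SAP*

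**What the plan says.** Section 5 (Study Design) holds the whole eligibility rule. It takes consecutive adults with symptomatic paroxysmal AF, treated by one operator, who "underwent a first-time cryoballoon ablation using either PVI alone or PVI+PWI" and have at least 36 months of follow-up. The one explicit exclusion is that "all patients with persistent or long-standing persistent/permanent AF will be excluded from this analysis". Earlier ablation by another method is neither admitted nor excluded. These patients "will be included in this retrospective, non-randomized study", and the data come only from chart review.

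Section 7 (Statistical Methods) says that "Baseline patient demographics, procedural and clinical characteristics will be recorded for the entire cohort", without listing any of them. For efficacy it says: "For freedom from recurrent atrial arrhythmias, a Kaplan-Meier modeled analysis will be performed". No regression, matching, weighting or stratification is named. Section 6 gives the size: "The target sample size for this study is approximately 1,000 patients".

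**The concern.** Grammatically, 'first-time' attaches to the cryoballoon procedure and not to AF ablation in general. A patient whose radiofrequency isolation failed and who then had a first cryoballoon procedure meets the literal wording. Section 5 names the investigator and sub-investigators as abstractors, so the rule could be read in two ways.

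If redo patients entered, were more common in one arm, and had a different recurrence risk, the unadjusted comparison would be biased. The direction is unknown because no rule for choosing the procedure is given. A patient with earlier left-atrial lesions also does not receive a clean version of either lesion set, which blurs what the two arms represent.

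**Working it through.** **Reading the text.** Three places bear on the meaning.

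- Section 5: the wording leaves earlier non-cryoballoon ablation open. It does not say that such patients are wanted.
- Section 4: the rationale speaks of first-line use and of freedom from AF after a single procedure. These passages describe an indication and published results, so they do not settle eligibility, but they fit a cohort having its first AF ablation.
- Section 7: prior ablation is not named among the recorded characteristics, but neither is any other characteristic. The silence carries no information about this one.

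The plan states no figure for redo patients, so there is none to reproduce. The target of 1,000 comes with no effect size, power or allocation ratio.

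**How large could a bias be?** Inputs:

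- From the document: total of 1,000 (Section 6); two-sided 5% level (Section 7); long-term freedom from AF of 50–60% (Section 4), taken here as s0 = 0.55 for patients without earlier ablation.
- Assumed: 500 per arm; redo share p in each arm; redo recurrence hazard h times that of the others; no true treatment effect.

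Freedom in an arm: S = (1 − p)·s0 + p·s0^h. Apparent hazard ratio over follow-up: ln(S_A)/ln(S_B).

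For h = 2, s0² = 0.3025:

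- p = 0.10: S = 0.90 × 0.55 + 0.10 × 0.3025 = 0.5253
- p = 0.02: S = 0.98 × 0.55 + 0.02 × 0.3025 = 0.5451
- Ratio = ln(0.5253)/ln(0.5451) = 1.061; with the arms reversed, 0.943
- Events: 500 × (1 − 0.5253) + 500 × (1 − 0.5451) ≈ 465
- z = ln(1.061) × √(465/4) = 0.64, so the two-sided rejection rate is Φ(0.64 − 1.96) + Φ(−0.64 − 1.96) ≈ 9.8%

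| Redo shares | h | Freedom in the two arms | Apparent HR when truth is 1.00 | False-positive rate |
|---|---|---|---|---|
| 10% vs 2% | 2 | 0.5253, 0.5451 | 1.061 (reversed 0.943) | 9.8% |
| 10% vs 2% | 1.5 | 0.5358, 0.5472 | 1.035 (reversed 0.966) | 6.6% |
| 5% vs 2% | 2 | 0.5376, 0.5451 | 1.023 (reversed 0.978) | 5.7% |
| 5% vs 5% | 2 | 0.5376, 0.5376 | 1.000 | 5.0% |

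Taking s0 as 0.50 or 0.60 moves the first ratio only to 1.059 or 1.063. At time zero, before higher-risk patients are depleted, that scenario gives 1.10/1.02 = 1.078 (reversed 0.927).

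**The same on the risk scale.** Spurious difference = (difference in redo share) × (excess recurrence risk in redo patients), from 45% recurrence and 500 per arm:

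- 5-point imbalance, 10 to 20 points excess: 0.5 to 1 point; false-positive rate 5.3% to 6.2%
- 10-point imbalance, same excess: 1 to 2 points; 6.2% to 9.7%
- 20-point imbalance, same excess: 2 to 4 points; 9.7% to 24.5%

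For scale, 500 per arm gives about 82% to 85% power for a 9-point difference when freedom after PVI alone is 50% to 60%.

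**The case for a change.** The strongest case for a change is that the literal text admits redo patients, that Section 4 describes other people's results and not this cohort, and that nothing later in the plan is bound to catch an imbalance. Settling the rule before charts are read would also prevent decisions on borderline patients made with outcomes in view. If first-ever ablation is meant, writing it down costs one line.

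Much of this stands. The wording is open, no adjustment is stated, and a clarifying phrase would do no harm. A mixed cohort would also be harder to set beside published single-procedure results, even with equal shares.

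What does not stand is the step from an open phrase to a wrong result. It needs redo patients to be present, unevenly spread and prognostically different, and the document supports none of the three. The mechanism belongs to any unmeasured or unadjusted factor in a non-randomized study; tightening this criterion would leave every other one untouched. Nor is restriction the only sound answer, since admitting such patients and adjusting for earlier ablation is equally defensible. A chart field would also be imperfect, because an ablation done elsewhere may not appear in this hospital's record.

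**Conclusion.** No change is called for. This is a definition left unwritten, and the people applying it would probably read it as a first AF ablation performed with the cryoballoon. On that reading redo patients are not eligible and this route to bias is closed, apart from any earlier ablation missing from the chart.

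On the other reading, the effect is of unknown direction and probably small. An assumed fivefold imbalance with a doubled hazard moves a null hazard ratio by about 6%, and a 5% versus 2% imbalance moves it by about 2%. The false-positive rates of about 10% and above arise only at the far end of the assumed range, and the 24.5% figure needs a 20-point imbalance for which the document offers no basis. All of these rest on assumed shares, hazards or excess risks, and on a 1:1 split.

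The more consequential feature is that Section 7 states no confounder adjustment for a comparison Section 5 calls non-randomized. That should be judged on its own merits and does not depend on how this phrase is read.

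### Section 5 makes 36 months of follow-up a condition of inclusion without saying potential follow-up is meant; applied to charted follow-up, it drops early deaths from the safety rates

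*Combined protocol and SAP*

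**What the plan says.** Section 5 opens its inclusion sentence with "All consecutive patients with an age >18 years and symptomatic PAF who underwent a first-time cryoballoon ablation" and continues "using either PVI alone or PVI+PWI with at least 36 months of follow-up by a single operator", for procedures from 1/2014 to 12/2018. The 36 months are therefore part of the rule that decides who enters the cohort. The same section says that the data will be "exclusively obtained from retrospective chart reviews within the Cerner electronic medical record".

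Section 3.3 sets the safety aim: "To examine the acute and long-term adverse event rates associated with PVI+PWI versus PVI alone". Its list includes "Esophageal injury or atrioesophageal fistula" and death, and it defines one event by its status at hospital discharge.

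Section 4 also speaks of follow-up beyond 36 months, without saying whether it is observed or merely available. Section 7 names Kaplan-Meier for freedom from arrhythmia but gives no censoring rule. Section 6 says only "The target sample size for this study is approximately 1,000 patients". No section states a data cut.

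**The concern.** In a chart review, the person abstracting each record must decide whether a patient who died in month 2 belongs in the cohort. As worded, that patient does not have 36 months of follow-up and would be left out. Inclusion would then depend on something that happens after the procedure, and the cohort would no longer be consecutive.

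Safety is where this matters. A procedural death, or a complication that proves fatal before 36 months, would leave the data together with the patient. A non-fatal acute complication in a patient who later moves to another provider would go the same way. The study compares a more extensive ablation with a less extensive one and asks for acute as well as long-term event rates, so these are events it needs to report.

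Because the rule is open, two abstractors could also build different cohorts from the same charts, and the choice could be made after outcomes have been seen.

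**Working it through.** The plan has no figure of its own to reproduce here. The target of about 1,000 comes without effect size, power, allocation or dropout, and the point does not depend on it.

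**Step 1: the two meanings of the condition.**

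| | Charted follow-up of at least 36 months | Potential follow-up of at least 36 months |
|---|---|---|
| Death at month t < 36 | excluded | included |
| Leaves the record before month 36 | excluded | included, censored |
| Acute complication in such a patient | not counted | counted |
| Death after month 36, in the record | counted | counted |

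The left column follows from the wording and needs no assumed rate.

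**Step 2: dates under the potential reading.** The last eligible procedures, in 12/2018, reach 36 months by 31 December 2021. With a cut on or after that date the condition excludes nobody. The text itself cannot predate mid-2021, since it cites an article as "2021 Jul 13. doi: 10.1111/jce.15164. Online ahead of print". With a cut at the end of July 2021, procedures from August to December 2018 would fall short: 5 of 60 enrolment months, or 8% at even accrual. At the end of September 2021 it would be 3 of 60, or 5%. Exclusions of this kind follow the calendar and not the outcome.

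**Step 3: deaths removed under the charted reading.** The mortality m and loss l per year are assumptions, because the documents give neither.

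- Deaths before 36 months per 1,000 treated: 1,000 × [1 − (1 − m)³].
- Of these, deaths in the chart before loss: 1,000 × hd/(hd + hl) × [1 − exp(−3(hd + hl))], with hd = −ln(1 − m) and hl = −ln(1 − l).

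| m per year | Deaths removed | Charted, l = 5% | Charted, l = 12% |
|---|---|---|---|
| 0.5% | 14.9 | 13.8 | 12.4 |
| 1% | 29.7 | 27.5 | 24.7 |
| 2% | 58.8 | 54.5 | 48.9 |

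Worked example at m = 1%, l = 5%: hd = 0.01005, hl = 0.05129, sum 0.06134. Then 0.01005/0.06134 = 0.1638 and 1 − exp(−0.1840) = 0.1681. The product is 0.0275, or 27.5 per 1,000.

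**Step 4: deaths still counted after month 36.** Assume the data cut falls evenly between 36 and 96 months after the procedure, so retained patients have 0 to 5 further years. With h = hd + hl, the charted fraction dying is hd/h × [1 − (1 − exp(−5h))/(5h)].

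- m = 0.5%, l = 12%: 0.0377 × 0.2693 = 0.0102, about 5 per 500 retained.
- m = 2%, no loss: 0.0488, about 24 per 500 retained.

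**Step 5: charts needed for 1,000 patients who reach 36 months, at m = 1%.**

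- No loss: 1,000/0.99³ ≈ 1,030.
- Loss of 5% per year: 1,000/(0.95³ × 0.99³) = 1,000/0.832 ≈ 1,200.
- Loss of 12% per year: 1,000/(0.88³ × 0.99³) = 1,000/0.661 ≈ 1,510.

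**The case against.** The strongest reply is that potential follow-up was meant. Consecutive enrolment does not fit with dropping patients who die. Kaplan-Meier is chosen to handle unequal follow-up, and under the charted reading it would have no loss to censor before month 36. A plan that lists acute events and death is unlikely to intend leaving out early deaths. The 12/2018 close is consistent with a window chosen to let 36 months elapse. All of this stands as evidence of intent. None of it is an instruction to the abstractor, and the potential reading rests on a cut date that the protocol does not give.

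Three stronger conclusions might be inferred, and the documents support none of them.

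- *The sponsor chose to condition on survival.* The text is open between two readings and does not show which was intended.
- *The study would report no deaths.* The plan defines no 36-month mortality analysis, and deaths after month 36 are counted: about 5 to 24 per 500 retained in Step 4. What goes missing is procedural and early death, not all death.
- *Recurrence estimates or the arm comparison are biased.* That would require retention to depend on recurrence, and for the comparison, to do so differently by arm. The documents are silent on both, so neither presence nor direction of bias can be determined.

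It is also fair to say that every rate in Step 3 is assumed. The exclusion itself is not: under the charted reading all deaths before 36 months are removed, whatever the rate.

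**Conclusion.** The concern holds in conditional form and should be fixed. It is certain that 36 months of follow-up is a condition of inclusion and that its meaning is unstated. It is not certain which meaning was intended.

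Under the charted reading, early deaths and the complications of patients who die or leave early are lost from both the acute and the long-term safety rates. The size is about 15 to 59 deaths per 1,000 treated at assumed mortality of 0.5 to 2% per year, of which about 12 to 55 could be recovered from the charts at assumed loss of 5 to 12% per year. Under the potential reading with a cut at the end of 2021 or later, nothing is lost and the phrase is redundant.

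The gain from the change is complete reporting of charted early events. It is not a demonstrated correction to the efficacy result.

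**What to change.** In Section 5, define inclusion by procedure: all consecutive first-time cryoballoon ablations for symptomatic PAF from 1/2014 to 12/2018, with the other stated criteria unchanged. State a data cut no earlier than 31 December 2021, so that every patient has 36 months of potential follow-up, and say that no minimum actual follow-up is required. If the cut has to be earlier, end the procedure window 36 months before it.

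In Section 7, start time at the procedure, censor recurrence at last contact or data cut, and count deaths and adverse events from day 0 in all treated patients. Report deaths and losses before 36 months by arm.

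Cost: if potential follow-up was meant, the Section 5 change is a sentence and a date. If charted follow-up was meant and the 1,000 counts patients reaching 36 months, abstraction rises to about 1,030 charts with no loss, 1,200 at 5% loss per year and 1,510 at 12%, all at 1% mortality. If the 1,000 already counts treated patients, no extra charts are needed, and at those two loss rates about 170 to 340 patients are no longer discarded. Event rates may look less favourable, and the recurrence curves will still rely on non-informative censoring.

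### No confounder-adjusted comparison is prespecified for a non-randomized study, so case mix or procedure date could create or hide a difference between PVI+PWI and PVI alone

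*Combined protocol and SAP*

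**What the plan says.** Section 4 states a comparative purpose: "the aim of this retrospective, observational study is to examine the clinical efficacy and safety" of the two strategies. Sections 2 and 3 set the objective and all endpoints as PVI+PWI versus PVI alone.

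Section 5 defines the cohort as consecutive adults with symptomatic paroxysmal AF who had a "first-time cryoballoon ablation using either PVI alone or PVI+PWI with at least 36 months of follow-up by a single operator", "between 1/2014 and 12/2018", at one hospital. They "will be included in this retrospective, non-randomized study". The section does not say how the strategy was chosen for a given patient.

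Section 7 is the whole statistical plan. It states that "Baseline patient demographics, procedural and clinical characteristics will be recorded for the entire cohort" and names the t or Mann-Whitney test for continuous variables and the chi-square or Fisher test for categorical ones. For the outcome: "For freedom from recurrent atrial arrhythmias, a Kaplan-Meier modeled analysis will be performed". It adds "For all analyses, P-values will be two-sided", with significance at P<0.05. No test is named for comparing the curves.

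**The concern.** Without randomization, the two groups may differ in anything that influenced the operator's choice of strategy, and in anything that changed over the accrual period. Baseline characteristics are recorded, and the named tests can describe an imbalance. No later step in the plan uses the result, however, so as written an imbalance changes nothing in the efficacy or safety comparison.

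The error can go either way. If PVI+PWI patients were at lower risk of recurrence, the plan could declare a benefit that is not there. If they were at higher risk, it could hide a real one. The target of about 1,000 patients reduces random error but not this bias. For a fixed bias, more events make a falsely significant result more likely.

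**Working it through.** **1. Is adjustment planned anywhere?** The contents list runs from section 1 to section 8, and section 7 is complete prose. Neither it nor any other section contains a regression model, propensity score, matching, weighting, stratification, covariate list or allowance for procedure date.

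**2. The plan's own figure.** Section 6 gives only a total of about 1,000. No effect size, power, group split or event count is stated, so the figure cannot be reproduced. It does not bear on confounding.

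**3. Inputs for an illustration.**
- From the documents: 1,000 patients (section 6), two-sided 0.05 (section 7), and long-term success of 50–60% after PVI-guided cryoballoon ablation (section 4). The midpoint of 55% gives 1,000 × 0.45 = 450 recurrences.
- Assumed: equal arms, a log-rank test, and one binary risk factor with hazard ratio H, present in a proportion p1 of the PVI+PWI arm and p0 of the PVI arm. The documents supply neither the strength nor the prevalence of any confounder.

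**4. No true effect.**
- SE(log HR) = 1/√(450 × 0.25) = 0.0943.
- Apparent HR ≈ [1 + p1(H − 1)] / [1 + p0(H − 1)].
- With t = |ln(apparent HR)| / 0.0943, two-sided error = Φ(−1.96 + t) + Φ(−1.96 − t).
- Worked case, H = 2.0 and 30% vs 50%: 1.30/1.50 = 0.867; t = 1.52; error = 32.9%.

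| p1 vs p0 | H | Apparent HR | Error, formula | Error, simulated |
|---|---|---|---|---|
| 37.5% vs 42.5% | 1.5 | 0.979 | 5.6% | not run |
| 37.5% vs 42.5% | 2.0 | 0.965 | 6.7% | not run |
| 35% vs 45% | 1.5 | 0.959 | 7.3% | 7.7% |
| 35% vs 45% | 2.0 | 0.931 | 11.8% | 11.3% |
| 30% vs 50% | 1.5 | 0.920 | 14.3% | 13.7% |
| 30% vs 50% | 2.0 | 0.867 | 32.9% | 32.6% |

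The simulation used 10,000 runs per case, exponential times and administrative censoring. A balanced factor with H = 2.0 gave 5.1%. A log-rank test stratified on the factor gave 4.7–5.4% in every simulated case.

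**5. Sensitivity to events and split (simulated).**

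| Case | 400 events | 500 events | 25:75 arms |
|---|---|---|---|
| H 1.5, 10 points | 6.6% | 7.8% | 6.0% |
| H 2.0, 20 points | 29.0% | 34.9% | 23.4% |

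**6. Opposite direction.** The HR detectable with 80% power is exp(−2.80 × 0.0943) = 0.768, so take a true HR of 0.77. Simulated power with the risk factor more common in the PVI+PWI arm:

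| PVI+PWI vs PVI | H = 1.5 | H = 2.0 |
|---|---|---|
| Balanced | 78.7% | 77.1% |
| 45% vs 35% | 63.8% | 48.6% |
| 50% vs 30% | 46.5% | 22.4% |

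Stratifying kept 77.1–78.5% in the imbalanced cases. The formula agrees roughly: for H = 2.0 and 50% vs 30%, the apparent HR is 0.77 × 1.50/1.30 = 0.888, and power is Φ(0.1184/0.0943 − 1.96) = 24%.

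**7. A second model.** Take a two-proportion z test with 500 per arm, overall freedom of 55% and no true effect. With a factor present in 60% vs 40% of the groups, error is 9.7% if freedom is 60% without the factor and 50% with it. It is 24.6% if freedom is 65% and 45%. The conclusion is the same.

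**The case against.** The strongest reply is that no bias has been shown. The documents report no imbalance, no selection rule and no shift in technique over time, and the cohort is already restricted in ways that remove operator, site, redo and AF-type differences. This is correct. It means that procedure date is an uncontrolled possibility, not a documented fact, and that high confidence attaches to the omission and not to the size of its effect.

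The larger figures also need a strong factor and a 20-point imbalance. A 5-point imbalance costs little (5.6% or 6.7%). That stands too, which is why mild and strong cases are shown together.

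The power figures hold the event count at 450. If freedom with PVI alone is 55% and the true HR is 0.77, recurrence with PVI+PWI is 1 − 0.55^0.77 = 36.9%. That gives 500 × (0.45 + 0.369) ≈ 409 events and unconfounded power of about 75%. With 50% freedom, inside the protocol's range, the count is about 457 and power about 80%. The loss from confounding is in the same direction either way.

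Finally, section 7 does not forbid adjustment. But choosing covariates or a method after outcomes are known allows selection among results, so silence does not protect the comparison.

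**Conclusion.** The concern holds and should be fixed before the analysis is run. The objective is comparative, assignment was not randomized, and the only planned analyses are unadjusted, with a P<0.05 rule. A significant or null result under this plan could not be attributed to the technique rather than to patient selection or era.

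The actual bias cannot be sized from the documents. In the simulated scenarios with equal arms and 450 events, one unbalanced factor raises the false-positive rate from 5% to between 7% and 33%, or cuts power from just under 80% to between 64% and 22%. Those ranges rest on the assumed factor strengths (HR 1.5 to 2.0) and imbalances (10 to 20 points). Smaller imbalances do less harm. Adjusting for the factor restores the error rate and nearly all the power, but only for factors that are measured.

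**What to change.** **Needed.** In section 7, before outcomes are examined:
- Make the primary comparison an adjusted hazard ratio with 95% CI from a Cox model. It may be multivariable or propensity-score weighted; choose one in advance.
- Fix the list of pre-procedure covariates and include procedure date. Age, sex, comorbidities, AF duration, left atrial size, LVEF and prior antiarrhythmic drugs are suggestions only, because the documents name no variables and do not say which are in the chart.
- Leave out consequences of the technique, such as procedure time or number of freezes.
- Report standardized differences and the overlap of the two techniques by calendar time. If they hardly overlap, state that technique and era cannot be separated.
- Keep the unadjusted Kaplan-Meier curves as descriptive, and word conclusions as associations.

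**Optional.** Add a sensitivity analysis for unmeasured confounding, such as an E-value, and adjusted safety comparisons where event counts allow.

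**Cost.** One paragraph, modest extra analysis and some extra chart abstraction. The adjusted interval may be wider, and the estimate may move in either direction.
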